### 4.3 Exclusion Criteria

An adult who meets any of the following exclusion criteria at screening will not be eligible for randomization in the study:

1. Use of any investigational medicinal product within 90 days prior to randomization or planned use of such a product during the period of study participation.
2. Adults who have previously been vaccinated against *S. pneumoniae*.
3. History of microbiologically confirmed invasive disease caused by *S. pneumoniae*.
4. History of allergic disease (including angioedema) or history of a serious reaction to any prior vaccination or known hypersensitivity to any component of the study vaccines, including PEG.
5. Any abnormal vital sign deemed clinically relevant by the PI.
6. Acute illness at time of randomization (moderate or severe) and/or fever (body temperature of  $\geq 38.0^{\circ}\text{C}$ ) see note below.
  - a. Note: A minimum of 48 hours following a documented fever must pass before the participant can be vaccinated.
7. History of any non-study vaccine administration within 14 days of study vaccine administration.
8. No planned vaccines until after Day 29 (Visit 3).
9. Chronic administration (defined as more than 14 consecutive days) of immunosuppressant or other immune modifying drugs prior to the administration of the study vaccine (and within the 6 months prior to administration of the study vaccine), including the use of glucocorticoids. The use of topical and inhaled glucocorticoids will be permitted.
10. Administration of immunoglobulins and/or any blood products within the 6 months prior to administration of the study vaccine or anticipation of such administration during the study period.
11. Any medical or social condition that in the opinion of the PI\*, may interfere with the study objectives, pose a risk to the participant, or prevent the participant from completing the study follow-up.
12. Any screening laboratory test result outside the normal range and with toxicity score  $\geq 2$ , unless allowed by the PI, IVT Chief Medical Officer (CMO), and PATH Medical Officer (MO). A participant may repeat each laboratory assessment once during the screening period, with the most recent laboratory value being used for evaluation of exclusion criteria.
13. A positive serologic test for human immunodeficiency virus (HIV)-1 or HIV-2 (HIV 1/2 Ab), hepatitis B (HBsAg) or hepatitis C (HCV Ab).

\* The term "PI" is used throughout this protocol to refer to either the PI or designee.

14. History of malignancy, excluding non-melanoma skin and cervical carcinoma in situ.
15. Recent history (within the past year) or signs of alcohol or substance abuse.
16. History of major psychiatric disorder.
17. Female adult participants who are pregnant or breastfeeding.
18. Participant is an employee of, or direct descendant (child or grandchild) of any person employed by the Sponsor, PATH, the Contract Research Organization (CRO), the PI.

## **5. STUDY PRODUCTS**

### **5.1 IVT PCV-25**

#### **5.1.1 Product Description**

The 3 doses of IVT PCV-25 selected for the Phase 2 trial

[REDACTED]

Formulation A:

[REDACTED]

Formulation B; 2.2/250:

[REDACTED]

Formulation C; 4.4/250:

[REDACTED]

#### **5.1.2 Manufacturer**

IVT PCV-25 is manufactured and supplied by Inventprise, Inc.

#### **5.1.3 Presentation and Formulation**

IVT PCV-25 will be supplied in a five-dose vial, in cartons containing 10 labeled vials. Each vial label will include the following information in both English and French: name of the medicinal product, strength, dose and dose volume, route of administration, lot number, retest dates, storage

condition, a cautionary statement (“For Human Clinical Trial Use Only”), and the Sponsor’s name and address.

#### **5.1.4 Storage**

IVT PCV-25 should be stored between 2°C and 8°C. It must not be frozen.

#### **5.1.5 Potential Safety Risks**

As with any vaccine, severe allergic reaction is a potential rare event. Known hypersensitivity to any component of the vaccine (including diphtheria toxoid, CRM197, and PEG) is a contraindication to vaccination.

### **5.2 Prevnar 20™**

#### **5.2.1 Product Description**

Prevnar 20™ is approved for use in adults in Canada. A single 0.5 mL dose of Prevnar 20™ contains approximately 2.2 µg of each of *S. pneumoniae* serotypes 1, 3, 4, 5, 6A, 7F, 8, 9V, 10A, 11A, 12F, 14, 15B, 18C, 19A, 19F, 22F, 23F, 33F saccharides, 4.4 µg of 6B saccharides, all conjugated to CRM197 and adsorbed onto aluminum phosphate (0.125 mg aluminum). The vaccine is a turbid white suspension.

#### **5.2.2 Manufacturer**

Prevnar 20™ is manufactured by Wyeth Pharmaceuticals, a subsidiary of Pfizer.

#### **5.2.3 Presentation and Formulation**

Prevnar 20™ is supplied in a single dose 0.5 mL glass pre-filled syringe (PFS) with a plunger stopper and protective tip cap. It will be labeled with the following minimum information: name of the medicinal product, route of administration, expiry date, lot number, and dose volume.

#### **5.2.4 Storage**

Prevnar 20™ should be stored between 2°C and 8°C. It must not be frozen.

#### **5.2.5 Potential Safety Risks**

Hypersensitivity to any component of the vaccine (including diphtheria toxoid and CRM197) is a contraindication. For Prevnar 20™, in adults 18 years of age and older, the most commonly reported solicited adverse reactions (>10%) were pain at the injection site, muscle pain, fatigue, headache, and arthralgia. Additionally, injection site swelling was also reported (>10%) in adults 18 through 59 years of age.

### **5.3 Vaccine Storage, Transport, and Temperature Monitoring**

The temperature of study vaccines will be monitored during shipment and storage at the sites to ensure that temperature deviations do not occur.

The temperature of all vaccine shipments will be monitored throughout transit using a continuous temperature monitoring system. Vaccines will not be used until the temperature of the vaccines throughout transit has been confirmed to be within acceptable limits.

Upon receipt at the site, all vaccines will be stored at 2°C to 8°C in dedicated refrigerators that are locked, and not accessible to unauthorized personnel. The refrigerators will be under continuous temperature monitoring with maintenance of daily temperature logs and connected to a power source with a reliable back-up system.

It is the responsibility of designated unblinded site personnel to ensure that vaccine has not been exposed to temperatures outside the allowed range during transport or storage at the facility prior to being dispensed for vaccination. Should there be a deviation outside the allowed temperature range, the affected vaccine(s) will be quarantined. The temperature deviation will be reported to PATH and IVT, Inc. who will advise the unblinded study staff of the action to be taken based on the magnitude and duration of the temperature deviation. All vaccine accountability procedures, including cold chain monitoring will be documented and are the responsibility of the unblinded study personnel.

### **5.4 Dose Preparation and Administration**

Appropriately trained, unblinded study personnel will be responsible for preparing study vaccine doses in accordance with the randomly determined assignment, administering the study vaccines, and handling all vaccine accountability procedures. Unblinded personnel will not participate in the other aspects of the clinical trial after vaccine administration, to help ensure the integrity of the blind at the site. The unblinded personnel will not reveal participants' randomization assignments to the participants, or staff associated with the Sponsor, PATH, CRO, or site. Unblinded personnel will retrieve a participant's randomization assignment after being informed by the PI that a participant is eligible for randomization. They will prepare the study vaccine based on the participant's randomization assignment in a setting distinct from the study staff, and then the unblinded study nurse will administer study vaccine to a participant. All study personnel will be trained in immediate management of AEs following immunization including anaphylaxis. Vaccination will take place in a clinical setting in which there is immediate access to the medical personnel, equipment, and medications required for emergency resuscitation.

Since IVT PCV-25 and Prevnar 20™ are suspensions containing an alum adjuvant, study vaccine must be shaken gently immediately prior to use, in order to obtain a uniform homogenous white suspension. Inspection of each vial/PFS will occur immediately prior to use. If a vial/PFS or its contents appear unusual in any way, the vial/PFS will not be used, and procedures detailed in the Pharmacy Manual and Lab Manual for documentation and disposal will be followed. One separate

multi-dose single vial will be used for each participant randomized to be vaccinated with IVT PCV-25.

A detailed account of procedures related to preparation and administration of study vaccine will be included in the Pharmacy Manual .

- IVT PCV-25 or Prevnar 20™ will be administered to adults as an intramuscular injection into the mid-deltoid muscle of the participant's non-dominant arm.

Injectable vaccines may be given at other sites if there is a good reason to do so (e.g., local infection, or pre-existing swelling).

### **5.5 Accountability and Disposal**

Following vaccination, the single multi-dose vaccine vial/PFS will be labeled with the participant ID of the participant to whom the vaccine has been administered using prepared stickers. The person who administered the vaccine and the time and date of vaccine administration will also be documented in an appropriate vaccine accountability log on the day of vaccination. All used vials/PFS without the needle will be stored in a dedicated space that is accessible only to the unblinded site personnel and the unblinded CRO monitor (and ultimately disposed of after completion of the study).

In case a vial/PFS of vaccine is broken or unusable, the unblinded site personnel will promptly inform the unblinded monitor and store the vial/PFS for accountability, following all safety precautions. In case a broken vial/PFS cannot be stored safely for accountability, appropriate discard and documentation will be followed after consultation with the unblinded monitor. Study product prepared but not administered to participants, and all unused study product, will likewise be documented per drug accountability processes and discarded after the study is completed or terminated after notification by the CRO unblinded monitor.

The designated unblinded site personnel will maintain a complete and accurate inventory of study vaccines received (including the quantity of vaccines received, date of receipt, condition at receipt, temperature noted during transit), those administered, and any broken or destroyed.

The unblinded CRO monitor will visit the sites periodically throughout the trial to review and verify vaccine accountability records, as well as to ensure compliance with all trial procedures by the unblinded site personnel. After final vaccine accountability is completed by the unblinded CRO monitor, any used or unused vials/PFS of study vaccine will be destroyed at the site under the supervision of the unblinded site personnel.

## **6. STUDY PROCEDURES**

### **6.1 Recruitment**

Prospective participants will be recruited by study sites by means of 1) print and/or electronic media prompting calls by interested individuals to the site, 2) contacting individuals who have previously given permission to be contacted about future research studies, and 3) word of mouth. All recruitment materials will be approved by the center's Ethics Committee (EC) /Research Ethics Board (REB) prior to use. During recruitment telephone calls, prospective participants will be given information (e.g., some elements of inclusion and exclusion criteria) to help them decide whether to make an appointment to learn more about the study, and, if interested to take part in the informed consent process.

#### **6.1.1 Initial and Continuing Informed Consent**

Informed consent is the process of ensuring that study participants fully understand the purpose of the study, procedures, and benefits and risks. The informed consent process continues throughout the study. Key study concepts will be reviewed with the participant at designated times and as needed; this review process will be fully documented. Additionally, if any new information becomes available that, in the judgment of the Sponsor and/or the PI may affect participants' decision to continue in the trial, such information will be shared, and may be the basis for requiring a new consent form to be signed.

The Standard Operating Procedure (SOP) for informed consent will be followed at each study site. The participant will review the consent form and have adequate opportunity to discuss the study with an investigator or a qualified designee. The consent process will be documented in the participant's source documents and must comply with the International Conference on Harmonisation of technical requirements for registration of pharmaceuticals for human use (ICH) Good Clinical Practice (GCP) guidelines and any local regulatory requirements.

The consent form will be signed and dated by the person conducting the consent process, the participant, and investigator (if applicable per local requirements). A copy of the signed ICF will be provided to the participant and the original ICF will be filed with other participant records by the study staff.

The ICF will only be completed once at the time of enrollment and prior to screening (unless new information necessitating repeat consent is required).

Regardless of duration on study, ongoing willingness of participation will be documented in the source documents at each visit.

### **6.2 Study Visits**

General information:

- Study-specific procedures for participants are indicated in Appendix 1.

- Blood sample volumes at designated visits are detailed in Section 7.
- Participants will be reminded at each visit to contact the study staff to report any SAE occurring at any time during the study.
- Participant ID will be confirmed on day of each visit
- Scheduling of subsequent visits will occur at each visit.

### **6.2.1 Screening**

Once informed consent has been documented, the participant will be considered to be enrolled in the trial and may be screened to determine study eligibility. All inclusion/exclusion criteria must be assessed from data obtained within the screening period, unless otherwise specified in the eligibility criteria. After informed consent has been obtained, screening procedures will be performed.

The PI will use good clinical judgment in considering a prospective participant's overall eligibility. Individuals who are not deemed eligible will be recorded as screen failures, along with the basis for this determination, on the appropriate CRF. Individuals who screen fail may not be rescreened.

At screening, screening positive serum or urine pregnancy tests and laboratory test results outside the normal range and with toxicity score  $\geq 2$  are exclusionary unless allowed by the PI, IVT Chief Medical Officer (CMO), and PATH Medical Officer (MO) (see Appendix 4). During the defined screening period for adults, prospective participants may return once for repeat assessments to be reassessed for eligibility. The last measurement will be taken as the baseline for purposes of analysis.

Unscheduled clinical laboratory measurements may be obtained at any time during the study to assess any perceived safety issues.

### **6.2.2 Randomization and Vaccination Visit General Information**

1. Eligibility for vaccination will be confirmed based on review of inclusion/exclusion criteria. Any participant who cannot be vaccinated due to an acute abnormality (e.g.,  $\geq$  Grade 2 acute illness, or abnormal vital sign deemed clinically relevant by the PI) may return once the acute issue has resolved, if deemed appropriate by the PI. A minimum of 48 hours must have passed after a documented fever (body temperature of  $\geq 38^{\circ}\text{C}$ ) before a participant can be vaccinated.
2. Pregnancy testing (urine) will be collected from all women of childbearing potential (WOCBP).
3. At Visit 1, all participants will be randomized to a vaccine group if eligibility is confirmed by the investigator(s). The randomization ID will be recorded by unblinded study staff, who will maintain a list documenting the study vaccine assigned and administered to given randomization IDs in a secure location that is not accessible to blinded study staff. The participant will be referred to by a participant ID for the remainder of the study.

4. Approximately 50 mL of blood will be obtained by venipuncture for immunogenicity testing prior to the administration of the study product.
5. After the study product is administered, the participant will be observed by blinded study staff for at least 30 minutes post-vaccination.
6. Vital signs and any solicited AEs will be recorded at 30 (+10) minutes post-vaccination. See Appendices 2 and 3 for relevant severity grading scales.
7. During the observation period, the participant will be provided with a ruler, thermometer, and memory aid, and given instructions on how to complete the memory aid. The participant will be instructed to collect solicited AEs daily for seven days (the day of Visit 1 and the following six days) by recording them in the memory aid, preferably at approximately the same time each day. The participant will also be instructed to record unsolicited AEs and concomitant medications on the memory aid.
8. The participant will be instructed to call the study staff in the event of any severe (Grade 3) symptoms, if there is ongoing local or systemic reactogenicity on Day 8, or for any other health issues that require medical attention. The PI will assess the need to evaluate such events/issues at an unscheduled visit.

### **6.2.3 Visit 2 General Information**

1. Unsolicited AEs will be recorded, including assessment of relatedness to vaccination, severity, and outcome. Ongoing unsolicited AEs will be reviewed.
2. The completed memory aid will be reviewed with the participant for completeness and accuracy. Possible inaccuracies will be clearly documented.
3. Blood sample obtained for safety labs.

### **6.2.4 28-Day Post-Vaccination Visit (Visit 3)**

1. Unsolicited AEs will be recorded, including assessment of relatedness to vaccination, severity, and outcome. Ongoing unsolicited AEs will be reviewed.
2. The completed memory aid will be reviewed for completeness and accuracy. Possible inaccuracies will be clearly documented.
3. Approximately 50 mL of blood will be obtained by venipuncture for immunogenicity testing.
4. Pregnancy testing (urine) will be collected from all women of childbearing potential (WOCBP).

### **6.2.5 Six Month Post-Last Vaccination Visits (Visit 4)**

1. Participant will be contacted by telephone

2. Participant ID will be confirmed.
3. SAEs since the last visit will be recorded, including any concomitant medications taken for the AE. Any ongoing unsolicited AEs will be reviewed.
4. Participants will exit the study after completion of the Study Exit CRF.

#### **6.2.6 Interim Contacts and Visits**

Interim unscheduled contacts and visits (e.g., unscheduled visits) in between regularly scheduled follow-up visits may occur at any time at the request of the participant or as deemed necessary by the PI. All unscheduled interim contacts and visits will be captured in the participant's study records and on applicable CRFs.

#### **6.3 Participant Discontinuation Termination**

Participant discontinuation from study procedures prior to completion of the last study visit may occur for any of the following reasons:

- **Withdrawal** (defined as discontinuation initiated by a participant): Participation in the study is strictly voluntary. Participants have the right to withdraw their consent from study participation at any time and for any reason, without penalty. The participant may also withdraw due to an AE. Non-coercive attempts (e.g., phone calls) will be made to obtain AE data according to the schedule of events if the participant is willing to provide.
- **PI-initiated**: The PI may, at their discretion, discontinue a participant from the study if it is considered to be in the participant's best interest to do so (e.g., for safety concerns), or if the participant does not comply with the study requirements.
- **Lost to follow-up**: For participants who fail to attend scheduled visits, study staff are to make at least three attempts to contact the participant prior to considering the participant as lost to follow-up. These attempts should be recorded in the source documents.
- **Sponsor-initiated**: For example, if the Sponsor is obliged to end the study for administrative or any other reason, such as a recommendation by the DSMB based upon safety review.

Participants who discontinue prior to first administration of study vaccine will be replaced, whereas those withdrawn after first administration of study vaccine will not be replaced.

The reason for and date of participant discontinuation will be recorded in the relevant CRF. Before concluding the reason for the participant's discontinuation from the study, the PI should make every effort to investigate whether an AE may have been related to the participant's discontinuation from the study. For participants considered lost to follow-up, the discontinuation date for the participant to be captured on the Study Exit CRF page is the date of the participant's last completed study visit.

In the event of participant discontinuation from the study, reasonable efforts should be made to conduct the following procedures (unless participant consent to do so has been withdrawn):

- Update participant contact information.

- Review the memory aid if still in use prior to discontinuation.
- Update any AEs that remained ongoing at the time of the participant's last visit prior to discontinuation.
- Collect any new reportable AEs and concomitant medications since the participant's last visit, based on the protocol-defined reporting period at the time of discontinuation.
- Perform a targeted PE to evaluate any newly reported AEs since the participant's last visit.

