#### **6.5 Emergency Unblinding Procedure**

In the event of a medical emergency, the PI and/or site investigator may require that the blind be broken for the participant experiencing the emergency when knowledge of the participant's treatment assignment may influence the participant's clinical care. Every effort will be made not to unblind the participant unless it is considered absolutely necessary for the welfare of the participant. Prior to unblinding, the investigator is encouraged (to the extent possible, without jeopardizing the participant's health) to contact the Sponsor (or designee) to discuss the decision to break the blind.

The PI and/or site investigator will be expected to provide a rationale for the necessity of unblinding, based on the expectation that knowledge of the participant's treatment assignment will have a meaningful impact on the participant's medical care in the short term. If a participant's treatment assignment is unblinded, the participant will remain in the study and continue with protocol-defined

study visits and procedures, unless there is another reason for participant discontinuation. The decision to unblind will be communicated to all regulatory bodies as required. At the end of the study, documentation of all unblinded participants (and the rationale for unblinding) will be incorporated into the trial master file.

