## **8.3 AE Recording and Reporting**

All AEs will be recorded and reported after receipt of each study vaccine through 28 days post-vaccination (Visit 3). SAEs will be recorded throughout the entire study period.

The study staff must completely and promptly record each AE in the source documentation and on the relevant CRF, regardless of relationship to the vaccine administered or procedure as determined by the PI. The PI will attempt, if possible, to establish a diagnosis based on the signs and symptoms. When a diagnosis for the reported signs or symptoms is known, the PI will report the diagnosis as the AE, not the signs and symptoms. AEs will be classified by the Medical Dictionary for Regulatory Activities (MedDRA) term and by severity, relatedness, and outcome.

Reporting of AEs will follow the regulatory guidelines of Health Canada, the local ethics committees (ECs), WCG IRB, and the PATH Office of Research Affairs (ORA) in regard to requirements, processes, and forms.

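### Protocol 6.3 commits to scheduled AE contact after discontinuation only for self-withdrawal; participants removed by the PI get only an exit collection

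*Protocol*

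**What the plan says.** Protocol 6.3 names four routes out of the study: withdrawal by the participant, removal by the PI, loss to follow-up, and a Sponsor decision.

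- **Withdrawal.** This is defined as the participant's own decision, and it can include leaving because of an AE. Only this bullet promises continued contact: "Non-coercive attempts (e.g., phone calls) will be made to obtain AE data according to the schedule of events if the participant is willing to provide".
- **Removal by the PI.** Here the PI may "discontinue a participant from the study if it is considered to be in the participant's best interest to do so (e.g., for safety concerns", or may remove a participant who does not comply. The bullet says nothing about contact afterwards.
- **All routes.** "In the event of participant discontinuation from the study, reasonable efforts should be made to conduct the following procedures", unless consent to them has been withdrawn. The list covers contact details, the memory aid if still in use, ongoing AEs, a targeted examination, and new reportable AEs since the last visit, the last of these "based on the protocol-defined reporting period at the time of discontinuation".

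The primary endpoints in Protocol 2.2 include unsolicited AEs to 28 days and SAEs to 6 months. Protocol 8.3 adds the general rule that "SAEs will be recorded throughout the entire study period". Under Protocol 11.7 and SAP 4.8, data gathered before discontinuation are analysed, and missing safety data are not imputed (the Protocol excepts AE dates; SAP 5.6 removes that exception). Protocol 11.5.5 and SAP 4.6.5 set each denominator as the participants with data for that endpoint.

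**The concern.** Each participant receives one dose, on Day 1. A participant removed later has already had the full exposure, and the primary safety windows are still open. Read as written, someone who leaves for personal reasons on Day 10 is contacted on schedule if willing. Someone the PI removes that day over a suspected reaction has no stated contact after the exit collection.

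The stake is bias more than precision. If removal is prompted by safety, the unobserved time falls on participants whose later course matters most to the primary objective. The analysis does not make up for this: nothing is imputed, participants who leave after vaccination are not replaced, and neither document says how a partly observed window enters the denominator. Such a participant could be counted as having no SAE to Day 169 without having been asked. The results are meant to support going directly to a study in infants (Protocol 1.8), and under pause Rule 1 (Protocol 9.2) a single vaccine-related SAE is enough to convene the DSMB.

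**Working it through.** **1. The text by route of exit (Protocol 6.3)**

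| Route | AE contact on the schedule after exit | Exit collection |
|---|---|---|
| Participant withdraws | Stated, if willing | Yes, unless consent withdrawn |
| PI removes | Not stated | Yes, unless consent withdrawn |
| Lost to follow-up | Not stated; at least three contact attempts come first | As far as contact allows |
| Sponsor ends the study | Not stated | Yes, unless consent withdrawn |

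PI removal is the row where a reachable, possibly willing participant is singled out and has no stated later contact.

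**2. Time left uncovered**

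Inputs: vaccination on Day 1, Visit 3 on Day 29, Visit 4 on Day 169 (Protocol Table 9). Day 10 is an illustrative day of removal and is not taken from the documents.

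- Unsolicited AEs: 29 − 10 = 19 of 28 days.
- SAEs: 169 − 10 = 159 of 168 days.

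**3. Weight of one missed event**

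Inputs: groups of 40, 60, 80 and 40 (Protocol Table 8).

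- 1/40 = 2.5%; 1/60 = 1.67%; 1/80 = 1.25%.
- In the group of 80, the exact (Clopper-Pearson) 95% interval is 0 to 4.51% for 0/80 and 0.03% to 6.77% for 1/80.

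**4. Effect on the plan's detection probabilities**

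Protocol Table 12 uses P(at least one) = 1 − (1 − p)^n. For n = 60 and p = 5%, 1 − 0.95^60 = 0.9539, against the stated 0.954. All nine cells reproduce to within 0.001.

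The documents give no number of PI removals. As an assumption, suppose 2.5%, 5% or 10% of a group lacks a full window, at random:

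| Case | No loss | 2.5% | 5% | 10% |
|---|---|---|---|---|
| n = 60, p = 5% | 0.954 | 0.949 (n = 58) | 0.946 (n = 57) | 0.937 (n = 54) |
| n = 80, p = 1% | 0.552 | 0.543 (n = 78) | 0.534 (n = 76) | 0.515 (n = 72) |

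The largest drop shown is about 0.04. Random loss is therefore a minor matter. Loss that depends on safety is not measured by this calculation, and it is the reason for the point.

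**The case against.** The strongest reply is that the protocol is silent and does not order follow-up to stop. Nothing in 6.3 forbids further contact. Section 8 makes the PI responsible for detecting and documenting AEs and SAEs while the study lasts, 8.1 and 8.3 have SAEs recorded over the whole study, 6.2 has participants reminded to report any SAE, and 6.2.6 allows unscheduled contacts. The Withdrawal sentence may even be a limit: people taking back consent need careful terms for further contact, while people removed by the PI have not taken it back. The event that prompts a removal is also well captured, because the PI must look into whether an AE was related to the exit, update ongoing AEs and examine new ones.

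Much of this stands. The gap is an unstated commitment, confined to time after exit. But the general lines do not clearly settle what happens after a PI removal, and a site working from 6.3 will find scheduled contact under one route only.

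Several stronger readings are tempting and are not supported:

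- **That removed participants drop out of the safety analysis.** They remain in the safety population (Protocol 11.4.3) and their data to exit are used.
- **That the Sponsor route selectively removes people after a DSMB review.** The example there is "if the Sponsor is obliged to end the study for administrative or any other reason". Ending the study affects all groups, so the loss is not selective.
- **That a Sponsor stop at the DSMB review would cost 140 of 168 days for all 220.** The review follows the last participant's Visit 3. With up to 7 months per participant and about 10 in total, accrual lasts roughly 3 months. Assuming uniform accrual over 90 days, the average loss is 140 − 45 = 95 days (57%), and only the last enrolled lose 140.
- **That 6.3 contradicts 8.3.** The general SAE rule can be read as covering discontinued participants, so a conflict is not shown.
- **That the emergency-unblinding rule points the other way.** Section 6.5 does say that "the participant will remain in the study and continue with protocol-defined" visits and procedures, but it excepts anyone with another reason to discontinue. It sets no rule for discontinued participants.

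**Conclusion.** The point holds in a limited form. Protocol 6.3 states scheduled AE contact after exit for participant-initiated withdrawal only. For PI-initiated removal, where safety concerns are the named example, it provides only the exit collection. The rest of the 28-day and 6-month primary windows then has no stated contact, and what is missing can depend on safety.

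For a removal on Day 10 the gap is about 19 days for unsolicited AEs and 159 days for SAEs. One event missed in that time is 1.25 to 2.5 percentage points of a group. This rests on sites following 6.3 as written and on at least one such removal; the number is not given and may be small or zero. No figure in the plan changes. It is worth correcting because the remedy is cheap, not because the safety analysis fails without it.

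**What to change.** In Protocol 6.3, move the sentence on scheduled AE contact out of the Withdrawal bullet so that it applies to every vaccinated participant who discontinues, including those removed by the PI. State that contact continues to Day 29 for AEs and to Day 169 for SAEs, the latter by telephone, unless the participant withdraws consent for contact or contact is lost. The exit-collection list can stay as it is.

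The cost is one wording change and a few extra calls. Telephone contact is already planned for self-withdrawals and for Visit 4.
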